### 1.3 Summary of Clinical Studies

As of 31-March-2016, one clinical study (Protocol #: KBP5074-1-001, NCT02228733) has been completed and evaluated the safety, tolerability, and pharmacokinetics (PK) of KBP-5074 single dose administration in healthy male and female subjects. This was an open-label, parallel-group, single ascending dose study with a food effect panel. A total of 46 subjects received KBP-5074 at dose levels of 0.5, 1.0, 5, 10, and 30 mg in the fasting state and 10 mg in the fed state.

KBP-5074 was safe and well tolerated in healthy male and female subjects. There were no drug related adverse events (AE) reported during the study. There were no clinically meaningful trends noted based on safety laboratory assessments including the complete blood count and potassium levels, physical examinations, vital sign measurements or electrocardiograms (ECGs) during this study. No evidence of bone marrow suppression was observed with increasing drug exposure. Specifically, no clinically meaningful trends of the complete blood counts, (white blood cell, neutrophils, red blood cell, or platelets) with increasing drug exposure were observed. No gender difference of drug exposure was observed.

At the dose levels tested, the mean maximum concentration ( $C_{max}$ ) ranged from 9.37 ng/mL (0.5 mg) to 259.4 ng/mL (30 mg), area under the concentration-time curve from time 0 until 24 hours postdose ( $AUC_{0-24h}$ ) ranged from 162.5 ng\*hr/mL (0.5 mg) to 5016 ng\*hr/mL (30 mg), and area under the concentration-time curve extrapolated to infinity ( $AUC_{0-\infty}$ ) increased from 678.4 ng\*hr/mL (0.5 mg) to 28195 ng\*hr/mL (30 mg). The time to maximum concentration ( $t_{max}$ ) under fasted conditions varied from 4 to 7 hours suggesting relatively fast absorption of KBP-5074 following oral administration under fasted conditions. The average half-life is greater than 50 hours.

There is an ongoing clinical study (Protocol #: KBP5074-1-002, NCT02653014) that will assess the safety, tolerability, and PK of KBP-5074 multiple dose administration in healthy adults and subjects with mild to moderate CKD (defined as estimated glomerular filtration rate [eGFR]  $\geq 30$  and  $\leq 89$  mL/min/1.73 m^2).

Additional information regarding the clinical evaluation of KBP-5074 can be found in the IB.

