## 2 Study Objectives

### 2.1 Primary Objectives

The primary objectives of this study are:

- To evaluate the safety and tolerability of a single dose of KBP-5074 in HD and non-HD patients with severe CKD.
- To evaluate the PK of KBP-5074 following a single oral dose administration of 0.5 mg KBP-5074 in non-HD patients with severe CKD (defined as eGFR  $\geq 15$  mL/min/1.73 m^2 and  $\leq 29$  mL/min/1.73 m^2 based on the MDRD equation) in Part 1 of the study.
- To evaluate the PK of KBP-5074 following a single oral dose of 0.5 mg KBP-5074 administered to HD patients in Part 2 of the study. Pharmacokinetics will be evaluated during the following periods in Part 2:
  - During a single interdialytic interval (from approximately 0 to 44 hours postdose).
  - During a single dialysis session (from approximately 44 to 48 hours postdose).
  - Overall through washout (from the time of dose administration through 312 hours postdose, as data permit).

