**Figure 3-1 Study Design Schematic for Part 1**

Abbreviations: CRU = clinical research unit; PK = pharmacokinetic.

##### Part 2

[figure not shown]
In Part 2, a single cohort (Cohort 2) of 6 HD patients will receive a single dose of 0.5 mg KBP-5074 on the same day of HD (immediately after the HD). Following dosing, patients will be followed for 13 days for PK and safety assessments (see Table 12-2). The PK

samples will be obtained relative to dose administration as follows (All PK samples will be collected within  $\pm 5$  minutes of the nominal time unless otherwise specified):

- During the interdialytic interval (using a venous stick or cannula) immediately predose (at time 0 [-5 min]; collected immediately prior to dosing, but following the termination of a previous dialysis session), 2, 4, 6, 8, 10, 12, 18, and 24 hours postdose;
- During the second HD session at 44 (immediately prior to HD [using a venous stick or cannula; -5 min] and 5 minutes after the start of HD [inlet {arterial;  $\pm 1$  min} and outlet {venous;  $\pm 1$  min} samples]), 44.25, 44.5, 46, and 47 hours postdose, and at the end of the second HD session;
- Following dialysis at 48.5, 49, 50, 52, 72, 96, 120, 168, 216, 264, and 312 hours postdose.

[figure not shown]
A study design schematic for a Monday, Wednesday, Friday (MWF) and Tuesday, Thursday, Saturday (TTS) HD schedule for Part 2 is presented in [Figure 3-2](#) and [Figure 3-3](#), respectively.

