### 3.1.1 Rationale of Study Design

The PK, safety, and tolerability of a single dose of KBP-5074 (up to 30 mg) have been evaluated previously in healthy male and female subjects. The PK, safety, and tolerability of multiple doses of KBP-5074 are also currently being evaluated in patients with mild and moderate CKD. In Part 1 of this study, patients with severe CKD will be enrolled in order to evaluate safety, tolerability, and PK in this patient population. Hemodialysis patients are included in Part 2 of this study because they represent the target population and PK and

safety data are needed in this population to support further clinical development of KBP-5074.

Females are included because both males and females are well-represented in the target clinical populations. Inclusion of both genders allows assessment of the possibility of a gender difference in the PK profile requiring gender-specific dose adjustment(s) in future clinical trials. Pregnancy precautions are specified to minimize the risk of unintentional fetal exposure.

The single dose study design is typically used for patient studies. Patients will be closely monitored throughout the study. A cohort size of 6 patients receiving KBP-5074 for Part 1 (Cohort 1) and Part 2 (Cohort 2) was empirically selected based on feasibility.

The safety assessments for this study are accepted measures for ensuring safety of patients during a clinical trial. The timepoints allowed for collection of PK samples for determination of KBP-5074 concentration are considered appropriate given the currently available information.

In contrast to many small molecule drugs, KBP-5074 has a relatively long terminal elimination phase half-life ( $t_{1/2}$ ; average >50 hours). For a drug with a long  $t_{1/2}$ , limited PK information can be obtained during a single interdialytic interval. Elimination of KBP-5074 will occur over several days and multiple dialysis sessions. As such, a single interdialytic interval will represent a small portion of the overall concentration-time profile for KBP-5074.

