## Part 2:

The following PK parameters will be calculated using noncompartmental methods, whenever possible, based on plasma KBP-5074 concentrations during the initial interdialytic interval:

During Interdialytic Interval	
PK Parameter	Definition
$C_{max}$	maximum concentration
$t_{max}$	time to maximum concentration
$AUC_{0-24h}$	area under the concentration-time curve from time 0 until 24 hours postdose, calculated using the linear trapezoidal rule for increasing values, and the log trapezoidal rule for decreasing values
$AUC_{0-44h}$	area under the concentration-time curve from time 0 until 44 hours postdose, calculated using the linear trapezoidal rule for increasing values, and the log trapezoidal rule for decreasing values
$AUC_{0-ti}$	area under the concentration-time curve from time 0 until the last timepoint during the first interdialytic interval, calculated using the linear trapezoidal rule for increasing values, and the log trapezoidal rule for decreasing values
$\lambda_z$	apparent terminal elimination rate constant
$t_{1/2}$	terminal elimination phase half-life, calculated as $\ln(2)/\lambda_z$

The following PK parameters will be calculated using noncompartmental methods, whenever possible, based on plasma KBP-5074 concentrations during dialysis and overall:

During Dialysis	
PK Parameter	Definition
Inlet $AUC_{t0-t1}$	area under the concentration-time curve from start of dialysis ( $t_0$ ) to the end of dialysis ( $t_1$ ) based on inflow concentrations. AUC will be calculated using the linear trapezoidal rule for increasing values, and the log trapezoidal rule for decreasing values
Outlet $AUC_{t0-t1}$	area under the concentration-time curve from start of dialysis ( $t_0$ ) to the end of dialysis ( $t_1$ ) based on outflow concentrations. AUC will be calculated using the linear trapezoidal rule for increasing values, and the log trapezoidal rule for decreasing values.
Outlet:Inlet Concentration Ratio	ratio of outflow to inflow concentrations based on time-matched inflow and outflow samples
Outlet:Inlet AUC Ratio	ratio of Outlet $AUC_{t0-t1}$ to Inlet $AUC_{t0-t1}$
$CL_{D, Recovery}$	estimated hemodialysis recovery clearance, where: $CL_{D, Recovery} = \text{Amount Recovered in Dialysate} / \text{Inlet } AUC_{t0-t1}$

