$CL_D$	estimated hemodialysis clearance, where: $CL_D = Q * (C_i - C_o) / C_i$ $Q$ – Inlet blood flow, $C_i$ – Inlet concentration (arterial), and $C_o$ – Outlet concentration (venous)
$ER_D$	hemodialysis extraction ratio, where: $ER_D = (C_i - C_o) / C_i$ $C_i$ – Inlet concentration (arterial) and $C_o$ – Outlet concentration (venous)
$\lambda_z$	apparent terminal elimination rate constant, as data permit
$t_{1/2}$	terminal elimination phase half-life, calculated as $\ln(2) / \lambda_z$ , as data permit

Overall	
PK Parameter	Definition
$C_{max}$	maximum concentration
$t_{max}$	time to maximum concentration
$AUC_{0-t}$	area under the concentration-time curve from time 0 until the last quantifiable concentration, calculated using the linear trapezoidal rule for increasing values, and the log trapezoidal rule for decreasing values
$AUC_{0-\infty}$	area under the concentration-time curve extrapolated to infinity, calculated as: $AUC_{0-inf} = AUC_{0-t} + C_t / \lambda_z$
$\lambda_z$	apparent terminal elimination rate constant
$t_{1/2}$	terminal elimination phase half-life, calculated as $\ln(2) / \lambda_z$
$CL/F$	total body clearance, calculated as $Dose / AUC_{0-\infty}$
$V_z/F$	volume of distribution

Pharmacokinetic parameters will be calculated using a validated software program such as WinNonlin version 6.4 or higher. Additional PK parameters may be calculated or compartmental analysis may be performed, as appropriate, to fully characterize available data.

Additional details regarding the PK parameter calculations are presented in the Statistical Analysis Plan (SAP).

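### The 'terminal' rate constant and half-life planned for the dialysis session rest on about 4 h of samples: they are not terminal, and if dialysis removes little drug the reported half-lives would be a subset selected toward faster elimination

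*Protocol*

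**What the plan says.** Section 7.1 lists Part 2 parameters for three periods: the interdialytic interval, dialysis, and overall. Each list contains λz and t1/2 under the same symbols and the same 'terminal' names. In the dialysis list the rate constant is the "apparent terminal elimination rate constant, as data permit", and t1/2 is ln(2)/λz with the same qualifier. These values are "based on plasma KBP-5074 concentrations during dialysis and overall". Section 2.1 places the session at about 44 to 48 h after dosing. The synopsis names the same two parameters during dialysis.

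The session samples (section 3.1, Part 2) are one immediately before dialysis at 44 h, one 5 minutes after the start, and then "44.25, 44.5, 46, and 47 hours postdose, and at the end of the second HD session". Sampling continues to 312 h.

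On the drug itself, section 1.3 states: "The average half-life is greater than 50 hours". Section 3.1.1 accepts that for such a drug "limited PK information can be obtained during a single interdialytic interval", an interval of about 44 h.

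Section 7.1 leaves further calculation details to the SAP, which is not among the documents reviewed. Section 7.7 says missing data are not imputed. Section 7.7.1 lists and summarizes Part 2 parameters for each of the three periods.

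**The concern.** There are two faults, and the second depends on conditions.

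- **Label.** A slope over 44 to 48 h, in the middle of a profile followed to 312 h, is not a terminal phase, whether or not dialysis removes drug. Three different quantities will carry one name and one symbol.
- **Selection.** Over 4 h a drug with a 50 h half-life barely declines, so by chance some patients will show a flat or rising slope. Such a slope gives no meaningful half-life. A summary of the half-lives that can be calculated then leaves out the slow-looking patients and keeps those that look fast by chance.

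Part 2 is meant to show, among other things, whether dialysis removes the drug. The artefact is largest when removal is nil, and it then points toward removal. A short on-dialysis half-life tabulated beside a longer interdialytic one could be misread in that way.

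**Working it through.** **Inputs from the protocol**
- Half-life above 50 h (1.3). I use 50 h, which favours the plan, because a longer half-life makes the slope harder to estimate.
- At 0.5 mg, AUC0-∞ "increased from 678.4" ng·h/mL and AUC0-24h "ranged from 162.5" ng·h/mL (1.3).
- Session times 44, 44.083, 44.25, 44.5, 46, 47 and 48 h, taking the end of dialysis as 48 h.
- 6 patients in Part 2 (5.1).

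**Assumptions not in the documents:** residual CV of 3% to 15%; blood flow of 300 to 400 mL/min; extraction ratio of 0 to 0.2; a one-compartment decline with F = 1; healthy-subject values carried over to dialysis patients.

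**1. The plan's own half-life.** AUC from 24 h to infinity is 678.4 − 162.5 = 515.9 ng·h/mL. For a log-linear tail, t1/2 = ln(2) × 515.9 / C24. C24 is not given. If it equals the 0-24 h average (162.5/24 = 6.77 ng/mL), t1/2 is 53 h; for C24 from 6 down to 4 ng/mL it is 60 to 89 h. This agrees with a value above 50 h but cannot be reproduced exactly.

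**2. Expected fall in 4 h.** 1 − 2^(−4/50) = 5.4%; at 70 h it is 3.9%, at 100 h 2.7%.

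**3. Precision of the slope.** λ = ln(2)/50 = 0.01386 per h. For the 7 times, Sxx = 15.5 h². SE = √ln(1+CV²) / √Sxx. At 5% CV this is 0.0500/3.94 = 0.0127 per h, nearly as large as λ.

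**4. Wrong sign and selection, no removal.** With a = λ/SE, P(slope ≤ 0) = Φ(−a). For at least one of 6 patients it is 1 − (1 − P)^6. The mean of the positive slopes is λ + SE·φ(a)/Φ(a).

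| Residual CV | SE (per h) | P(slope ≤ 0) | At least 1 of 6 | Mean kept slope / truth | Median kept t1/2 |
|---|---|---|---|---|---|
| 3% | 0.0076 | 3% | 19% | 1.04 | 49 h |
| 5% | 0.0127 | 14% | 59% | 1.23 | 43 h |
| 10% | 0.0253 | 29% | 87% | 1.89 | 30 h |
| 15% | 0.0379 | 36% | 93% | 2.59 | 22 h |

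Simulation of 400,000 profiles at each of 5%, 10% and 15% CV reproduces these figures. When all signed slopes are kept, the mean is 1.00 times the truth.

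Using only the 6 samples drawn during dialysis (Sxx = 13.2 h²) gives 16% and 31% non-positive slopes and ratios of 1.28 and 2.0 at 5% and 10% CV, so the choice of points matters little.

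**5. If dialysis does remove drug.** CL/F = 500,000 ng / 678.4 ng·h/mL = 0.737 L/h. V/F = 0.737 × 50 / ln(2) = 53 L. On dialysis, λ = (0.737 + Q·ER)/53. For example, Q = 300 mL/min = 18 L/h with ER 0.05 adds 0.9 L/h, and t1/2 is 22.5 h. The ranges below cover 300 to 400 mL/min.

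| Extraction ratio | On-dialysis t1/2 | Ratio at 5% CV | at 10% CV | at 15% CV |
|---|---|---|---|---|
| 0 | 50 h | 1.23 | 1.89 | 2.59 |
| 0.02 | 30-34 h | 1.05-1.07 | 1.36-1.44 | 1.76-1.89 |
| 0.05 | 19-22 h | 1.00-1.01 | 1.11-1.18 | 1.31-1.45 |
| 0.1 | 12-14 h | 1.00 | 1.01-1.04 | 1.08-1.16 |
| 0.2 | 7-8 h | 1.00 | 1.00 | 1.00-1.02 |

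**The case against.** A reader might infer that the plan drops wrong-sign slopes, so that biased values are certain. The text does not say this. It leaves its qualifier undefined and refers calculation details to the SAP, where acceptance rules for λz commonly sit. What does not depend on the SAP is narrower: ln(2)/λz has no meaning at a zero or negative slope, so any half-life summary leaves those patients out. Whether the rate constant itself is also selected is open.

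A reader might also take the no-removal figures as the expected error. They are not. The half-life above 50 h comes from healthy subjects off dialysis, the on-dialysis rate is the unknown, and no assay or residual CV is stated. With appreciable extraction or a 3% CV the bias is small.

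The likely harm is also limited:
- No comparison of half-lives between periods is planned; section 7.7.1 is descriptive.
- CL_D, CL_D,Recovery, ER_D and the outlet:inlet ratios do not use this slope. An ER_D near zero beside a short half-life would be a visible conflict.
- Section 7.7 requires n and full listings, so absent values would be noticed.
- Within the Part 2 parameter tables, only these two rows carry the qualifier, so the authors saw some difficulty. The caution in section 3.1.1 concerns the interdialytic interval, although the session is one eleventh as long (4 h against 44 h).

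These points stand as limits on size. They do not repair the label, and reporting n shows that values are missing without correcting a mean or median taken over the rest. An on-dialysis rate constant is a legitimate descriptor, so deleting it is not required.

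**Conclusion.** The point holds in limited form. The 'terminal' label is wrong on the protocol's own facts. The selection effect follows whenever a patient's slope is non-positive and half-life is summarized only where it can be calculated. Its direction is fixed, toward faster elimination. Its size is not: from about 1.0 (a CV near 3%, or extraction of about 0.1 to 0.2 or more) to about 2.6 (no removal, 15% CV, true half-life 50 h). It is thus largest in the case where it could falsely suggest removal. These sizes rest on the assumed CV, blood flow and extraction, and on carrying the healthy-subject half-life over to dialysis patients. The documents do not support saying that the plan prescribes dropping slopes, or that the dialysability assessment as a whole is compromised. Two descriptive values in 6 patients are affected.

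**What to change.** In section 7.1 (During Dialysis) and the synopsis:

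- Rename the two items intradialytic apparent rate constant and intradialytic apparent half-life, with symbols distinct from λz and t1/2.
- State that inlet samples are used, and whether the 44 h pre-dialysis venous sample is included.
- Summarize the rate constant for all patients with session data, whatever its sign, with its SE.
- Give the half-life only as ln(2) divided by the mean signed slope, or with the number estimable out of the number dosed. If the mean slope is itself not positive, report the half-life as not estimable. This can happen: at 10% CV with no removal, the SE of a mean over 6 patients is 0.0253/√6 = 0.0103 per h against a true 0.0139.
- State that the conclusion on dialysability rests on CL_D, CL_D,Recovery, ER_D and the outlet:inlet AUC ratio.

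Dropping the two parameters is an acceptable alternative. The cost is a wording change and a small change to one table, with no extra samples and no data lost.

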## 7.2 Safety Variables

The safety analysis will include physical examination findings, vital signs (blood pressure, pulse rate, respiratory rate and oral temperature), 12-lead ECGs, clinical laboratory findings (hematology, clinical chemistry, and urinalysis), and assessments of AEs. Safety data will be listed and summarized as detailed in the SAP.

## 7.3 Pharmacodynamic Variables

The pharmacodynamic (PD) analysis will include assessments of the change from baseline in concentrations of plasma aldosterone and serum potassium after single doses of KBP-5074. Pharmacodynamic data will be listed and summarized as detailed in the SAP.

## 7.4 Sample Size Calculations

No formal sample size calculations were performed. The sample size is based on what will provide sufficient data to obtain a PK profile. A total of 12 patients, both male and female patients with CKD, are planned for enrollment in the study.

## 7.5 Analysis Populations

The following analysis populations will be used in the statistical analyses.

Safety Population: The Safety Population will consist of all patients who receive any study drug. All analyses using the safety set will group patients according to treatment actually received.

Pharmacokinetic Population: The PK Population will consist of all patients who receive study drug and have adequate concentration-time data for the determination of PK parameters. All PK analyses will be performed using the PK Population.

Pharmacodynamic Population: The PD Population will consist of all patients who receive study drug and have at least 1 postdose PD concentration of aldosterone and potassium. All PD analyses will be performed using the PD Population.

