### 2.2 Secondary Objectives

The secondary objective of this study is:

- To evaluate the changes in plasma aldosterone and serum potassium from baseline levels following KBP-5074 dosing in patients with severe CKD and HD patients in Part 1 and Part 2, respectively.

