### 6.1.5 Clinical Laboratory Tests

Laboratory measurements (including hematology, clinical chemistry, and urinalysis) will be performed at the timepoints specified in [Table 12-1](#) and [Table 12-2](#) for Part 1 and Part 2, respectively. Clinical laboratory parameters for analysis are presented in [Table 6-1](#).

Serum potassium levels of study patients will be closely monitored throughout this study. To ensure quick access to laboratory results, serum potassium levels will be tested in local laboratories in this study. If serum potassium is  $>5.6$  mmol/L during a scheduled/unscheduled visit, serum potassium levels should be repeated as early as feasible (no more than 48 hours). For patients who currently take potassium supplementation, it is recommended that the repeat test of serum potassium be taken 24 hours after the stopping of potassium supplementation if the Investigator considers it clinically safe and feasible.

A single repeat of laboratory testing at Screening and Day -1 are allowed to rule out lab error (i.e. hemolysis in potassium specimens).

Urine or serum pregnancy tests (all female patients) and FSH tests (postmenopausal female patients) will be performed at the timepoints specified in [Table 12-1](#) and [Table 12-2](#) for Part 1 and Part 2, respectively.

An alcohol breath test and drug screen will be administered to all patients at the timepoints specified in [Table 12-1](#) and [Table 12-2](#) for Part 1 and Part 2, respectively.

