## 7.7 Statistical Analysis Methodology

Statistical analysis will be performed using SAS® software Version 9.3 or higher. All continuous variables will be summarized using the following descriptive statistics: n, mean,

standard deviation, median, minimum value, and maximum value. Categorical variables will be summarized using the following descriptive statistics: frequency counts and percentages. All data will be listed in data listings.

Further details of the statistical analyses, methods, and data conventions are described in the SAP. The SAP will be prepared by DaVita Clinical Research and approved by the Sponsor. This document may modify the plans outlined in the protocol; however, any major modifications of the primary analysis will also be reflected in a protocol amendment. Additional statistical analyses other than those described in this section may be performed if deemed appropriate in the plan.

The general principles listed below will be applied throughout the study:

- Unless otherwise stated, continuous data will be summarized with the following descriptive statistics: number of non-missing observations (n), mean, standard deviation (SD), median, minimum, and maximum. For categorical variables, frequencies and percentages of patients will be presented.
- All study data will be included in the individual patient data listings. All summary tables will present descriptive statistics for the parameters to be analyzed, wherever applicable.
- Missing data will not be imputed but will be analyzed as missing.

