### **7.7.3 Pharmacodynamic Analyses**

The change from baseline in concentrations of plasma aldosterone and serum potassium after single doses of KBP-5074 will be summarized by study part and cohort, and at each scheduled time point using descriptive statistics (n, mean, SD, median, minimum, and maximum).

The baseline value is the last value observed prior to first administration of study drug and any values after first administration of study drug are regarded as post-baseline values. The change-from-baseline variables will be calculated as the post-baseline value minus the value at baseline.

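### The single PD Population requires postdose values of both aldosterone and potassium, so a patient with no usable postdose aldosterone also drops out of the PD potassium summary

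*Protocol*

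**What the plan says.** Section 2.2 gives one secondary objective with two markers: "To evaluate the changes in plasma aldosterone and serum potassium from baseline levels following KBP-5074 dosing in patients with severe CKD and HD patients".

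Section 7.5 sets a single entry rule for the analysis of both. Patients must have received study drug and "have at least 1 postdose PD concentration of aldosterone and potassium". The next sentence makes this the only set for that work: "All PD analyses will be performed using the PD Population".

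Section 7.7.3 describes the analysis: "The change from baseline in concentrations of plasma aldosterone and serum potassium after single doses of KBP-5074 will be summarized by study part and cohort", at each scheduled time, using n, mean, SD, median, minimum and maximum. No analysis combines the two markers.

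The footnotes on biomarker samples in Tables 12-1 and 12-2 list 12 postdose times, from 2 to 312 hours, for aldosterone and potassium alike. Section 6.1.5 says of potassium that "serum potassium levels will be tested in local laboratories in this study".

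**The concern.** The conjunction in Section 7.5 makes a patient's place in the potassium analysis depend on having an aldosterone result. Nothing in the design calls for that link. One marker is measured in plasma and the other in serum, potassium is run locally for speed, and the two are reported in separate summaries. Failure of one assay says nothing about the validity of the other.

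A programmer who applies the text as written would set one population flag per patient and use it for both summaries. A patient with valid potassium at every visit but no usable postdose aldosterone would then be missing from the potassium change table. Potassium change is half of the secondary objective, and with six patients in a part each one counts. The rule works the other way too: a patient with aldosterone but no postdose potassium would leave the aldosterone summary. Since potassium is tested locally, the aldosterone-to-potassium direction is the one worth describing.

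**Working it through.** The protocol gives no figure that depends on this rule, and Section 7.4 states that no formal sample size calculation was done. There is therefore nothing to reproduce, and the check is mainly one of text.

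**Inputs**
- Patients per part: 6 (Section 5.1).
- Scheduled postdose biomarker times: 2, 6, 12, 24, 48, 72, 96, 120, 168, 216, 264 and 312 h, which is 12 (footnotes to Tables 12-1 and 12-2).
- Scheduled postdose chemistry panels, which include potassium (Table 6-1): 6 h and Day 14 (312 h), which is 2. The intermediate laboratory samples in Part 1 are for creatinine only (Table 12-1, footnote 5).
- Missing data (Section 7.7): "Missing data will not be imputed but will be analyzed as missing".

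**Step 1: what triggers exclusion.** One usable postdose value of each marker is enough for entry. For a patient who completes the schedule, all 12 aldosterone values must be unusable while at least one potassium value is valid. A few failed aldosterone samples exclude nobody.

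**Step 2: share of a part lost from the PD potassium summary.**
- 1 patient: 1/6 = 16.7%.
- 2 patients with a shared failure: 2/6 = 33.3%.
- All 6: 6/6 = 100%, so that part would have no PD potassium summary.

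**Step 3: what remains for an excluded patient.** Section 7.7 puts all study data in the listings. Section 7.7.2 summarises laboratory data, including change from baseline, without reference to the PD Population. On the narrowest reading the chemistry panel covers 2 of the 12 postdose times, so 12 − 2 = 10 times have no potassium summary that includes this patient.

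**Step 4: how likely this is.** The protocol gives no failure rate for aldosterone. Purely as an assumption, let each patient independently have probability q of losing the whole postdose series. The chance that at least one of 6 is affected is 1 − (1 − q)^6:

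| q (assumed) | at least 1 of 6 |
|---|---|
| 0.02 | 11.4% |
| 0.05 | 26.5% |
| 0.10 | 46.9% |

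A true q could lie below this range. A lost shipment or failed batch would also break the independence assumption: fewer occasions, but several patients lost at once.

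**The case against.** The strongest reply is that the trigger is rare and the harm small. Every postdose aldosterone value must fail while potassium, drawn at the same times, survives. Early withdrawal would usually remove both. The analysis is descriptive, and Section 7.7 lets the SAP modify the protocol's plans, with an amendment needed only for major changes to the primary analysis. All of this stands and limits the weight of the point. It does not remove the defect: the protocol states the rule outright, and no other section relaxes it or provides a set for each marker.

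Four stronger readings are tempting, and the protocol does not support them.

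- *Potassium data are thrown away.* They are not. The listings keep every value, and the chemistry-panel results at 6 h and Day 14 stay in the laboratory summaries. Because local potassium testing is described under clinical laboratory tests, the serial values might also be read as laboratory data and summarised there, which would shrink the loss further.
- *Potassium safety monitoring is weakened.* The Safety Population is all dosed patients, and the repeat-test provision in Section 6.1.5 does not refer to the PD Population.
- *Precision falls by a definite amount.* At equal SD, going from 6 to 5 patients raises a standard error by a factor of √(6/5) = 1.095, but the protocol plans no standard error, interval or test for these data.
- *The set is also faulty because it does not require a baseline.* This changes no result. Section 7.7.3 defines the variable so that "The change-from-baseline variables will be calculated as the post-baseline value minus the value at baseline", nothing is imputed, and n counts non-missing observations. A patient without a baseline adds no change value and is not counted in n. The population count may exceed the analysed n, but the table shows that openly.

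**Conclusion.** The point holds as a small wording defect with a real but narrow consequence. As written, a dosed patient with no usable postdose aldosterone is excluded from the PD summary of potassium change despite valid potassium data. The size is 1 of 6 patients (16.7%) in the affected part, or more if the failure is shared. The loss is confined to one descriptive summary under the secondary objective.

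This rests on two assumptions. The first is that the conjunction is applied literally; it may have been meant loosely, but the text does not say so. The second is that a whole aldosterone series can be lost while potassium survives, for example through a lost shipment or a failed assay batch. The protocol gives neither a rate for this nor the laboratory that runs aldosterone. The SAP was not available for this check and may already separate the two analytes; if so, only the wording of Section 7.5 needs to be aligned with it.

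**What to change.** Replace the PD Population sentence in Section 7.5 with a definition for each analyte: for aldosterone and for potassium separately, all patients who received study drug and have one or more postdose values of that analyte. State that each analyte's summary uses its own set, and carry the same definition into the SAP.

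The cost is one sentence in each document and two population flags in place of one. It needs no extra samples, visits or patients. Make the change before the aldosterone results are available, so that it cannot appear to depend on them.
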